# V.7 Are all drugs or substances in this study being used within the FDA approved route of administration? Yes

### V.8 Drugs Used In Study:

| Nitroglycerin (Nitrostat)   |  |
|---|--|
|   |  |
| Name of Sponsor   |  |
| Investigator's Brochure Version   |  |
| Investigator's Brochure Date  |  |
| Planned Use in this Study   |  |
| Condition/Disease Indication(s)   | Vascular dysfunction   |
| Subject Population  | Obese adults age 18-49 with prediabetes  |
| Dose(s)   | 0.3 mg   |
| Administration  | Other: sublingual  |
| Dosing Regimen  | 0.3 mg once  |
| FDA Approved Use  |  |
| Approved Condition/Disease Indication(s)  | Refief of angina pectoris pain   |
| Approved Patient Population   | Angina pectoris  |
| Approved Dose(s)  | 0.3mg  |
| Approved Administration   | Other: sublingual  |
| Approved Dosing Regimen   | 0.3 mg   |
| Is this study intended to be reported to the FDA as a well-controlled study in support of a new indication or a significant change in the labeling for this product?  | No   |
| Is this study intended to support a significant change in the advertising for this product?   | No   |
| Does this planned use of the product in this study, taking into consideration the route of administration, the dosage level, and the subject population, significantly increase the risk (or decrease the acceptability of the risk) associated with the use of this product? | No   |
| Rationale:  | This is used to test the responsiveness of vascular smooth muscle to an exogenous nitric oxide vasodilator. Our subjects are healthy you and older adults. The dose is small and has a fast onset of action (1-3 mins) duration of action of 30 min. reference: Hardman JG, limbrid LE, eds. Gilmans The Pharmacolgical Basis of Therapeutics. 9th ed. New yourk: McGraw Hill, 1996. |

Name of Sponsor
Investigator's Brochure Version
Investigator's Brochure Date

Planned Use in this Study
Condition/Disease Indication(s)
Subject Population

Subject Population Obese adults age 18-49 years with prediabetes Dose(s) 1 and 10  $\mu$ g/mL/min intra-arterially

Administration

1 and 10 µg/mL/min intra-arterially
Other: intra-arterial via brachial artery

Dosing Regimen 1  $\mu$ g/mL/min intra-arterially for 6 min; 10  $\mu$ g/mL/min

intra-arterially for 6 min

Forearm vascular endothelial dysfunction

FDA Approved Use

| Approved Condition/Disease Indication(s)  | Hypertension   |
|---|--|
| Approved Patient Population   | Adults with hypertension   |

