### VII.E.1 Will subjects be randomized? Yes

VII.E.1.a Will any subjects be blinded to which study arm they have been assigned?

Yes

VII.E.1.b Does the protocol permit telling subjects their treatment assignment at the end of the entire study?

Yes

VII.E.1.c Describe the circumstances under which subjects will be told what study arm they have been assigned.

At the end of the study, or after an adverse event that the subject is withdrawn from the study.

VII.E.2 Describe randomization scheme/assignment including ratio such as 1:1, 2:1 etc.

Subjects will be randomized 2:1 to salsalate or placebo, respectively so their is 2/3 chance they will be randomized to salsalate and 1/3 to placebo. This scheme was chosen to ensure proper effect sizes can be determined in the salsalate group in this pilot study. The obese non-prediabetc group will not be randomized and only undergo baseline testing.

VII.E.3 Will any questionnaires, surveys, or written assessments be used to obtain data directly from subjects in this study?

Yes

VII.E.4 List all questionnaires, surveys, written assessments and ATTACH each one to the application. (NOTE: You are NOT prohibited from attaching copyrighted materials to this application)

Phone screening questionnaire
Demographics and Contact Info questionnaire
Health History questionnaire
Modifiable Activity Questionnaire (MAQ)

3 Day dietary record (CRU bionutrition)

Salsalate screening log

VII.E.5 Does this project involve creating any audiotapes, videotapes, or photographs?

No

VII.E.6 Provide a detailed description in sequential order of the study procedures following the consent process - DO NOT cut and paste from the Consent Document.

Describe study populations separately if they will be participating in different procedures - include CONTROL population if applicable.

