#### Visit 1 (3.5 hours): Consent and Screening

- a. Explanation of the study; reading and signing of written informed consent b. If subject consents but requires a 2-week washout for aspirin, salicylate, NSAID, vitamin, supplements, they will be scheduled to complete the Visit 1 in 2 weeks. If subject consents and no washout is needed, screening tests will be performed same day to determine eligibility by the following:
- i. Research staff will obtain resting vitals (blood pressure, heart rate)
- ii. Research staff will obtain anthropometrics including weight, height, waist and hip circumference with tape measure.
- iii. Research staff will obtain resting 12-lead ECG
- iv. Subject will fill out the Demographics and Health History survey, and the Modified Activity Questionnaire (MAQ)
- v. Research nurse or trained staff will obtain venous blood draw using butterfly needle for UIHC pathology labs:
- Creatinine, Lipid panel, TSH(4.5 ml blood- 1 light green PST tube)
- Complete blood count(4.5 ml blood- 1 lavender tube)
- Subject will undergo oral glucose tolerance test (OGTT): Subject will consume a beverage containing 75 grams of glucose. Blood samples will be collected at timed intervals of baseline, 1 hour and 2 hours after consuming beverage for glucose and insulin. Total blood collected for insulin and glucose for OGTT: 13.5 ml blood (4.5ml x 3 PST tubes).
- TOTAL blood collected for Visit 1: 22.5 ml (1.5 Tablespoons)

- Visit 2 (2 hours): Dietary food record, cerebral blood flow velocity
- a. Meet with CRU bionutritionist for instruction on 3-day dietary record to return on visit 3
- b. Middle cerebral artery blood flow velocity using transcranial dopper during the following protocol to measure cerebral vasoreactivity to hypercapnia:
- -After 3 min of normal breathing, subjects will perform 2, 30 second breathholds sparated by 3 min.
- -Next, After 3 min of room air breathing, 3 min of breathin 2%CO2, 3 min of breathing 4%CO2 (balanced with 21%O2 and N) will be performed followed by 3 min of room air breathing.
- c. Subject will be instrumented with 24 hour blood pressure monitor to wear home for 24 hours. Subject will return it to the investigators when come in for Visit 3. There is no long term follow up.
- Visit 3 (3 hours): 1st Baseline experimental visit (Blood, Endothelial cells, FMD, PWV and Retina scan)
- a. Subject arrives at the CRU between 7-10 am after overnight 8 hour fast

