- b. Subjects on vasoactive medications will be asked to hold medication on the morning of experimental visits but to bring the medications with them to be taken after the visit.
- c. Return 3-day dietary recall
- d. IV catheter, endothelial cell collection and blood sample: Subject will lie supine and research nurse will insert venous 18 G catheter into antecubital vein.
- e. Research staff or physician will perform J wire endothelial cell collection (3 wires) via 18 G catheter.
- f. After 20 min, nurse practitioner will then obtain blood samples thru catheter:
- Lipid panel, insulin, hs-CRP, salicylate, creatinine, AST/ALT (4.5 ml blood- light green PST tube)
- Catecholamines (8 ml blood- 2 x 4 ml Na+ Hep green top tubes)
- HbA1c (4.5 ml blood- 1 x 4.5 ml lavender top tubes)
- Extra blood collected for specialized labs performed in PIs lab:

Serum: 17 ml blood-  $2 \times 8.5$  red/gray top SST tube) for interleukin-6, tumor necrosis factor-alpha.

Whole blood (17 ml blood-  $3 \times 8.5$  ml Citrate PPT tube) for mononuclear cell DNA isolation.

- f. After 15 min supine rest the following non-invasive vascular measurments are obtained by the PI and his research staff:
- 1) Radial, brachial, carotid and femoral waveforms non-invasively for PWV assessment
- 2) Carotid artery compliance using ultrasonography
- 4) Brachial artery flow-mediated dilation (FMD) with ultrasound
- 5) Brachial artery dilation after 0.3 mg sublingual nitroglycerin with ultrasound
- g. Subject escorted to the CRU Human Cardiovascular Research Lab and a physician or research staff trained in microneurography will insert needle into peroneal nerve for measurement of muscle sympathetic nerve activity
- h. Subject will meet with bionutritionist and review 3-day food record with subject
- i. Subject receives meal/snack from CRU bionutrition and then can leave
- \*\*TOTAL blood collected for Visit 3= 68 ml (~4.5 tablespoons)

Visit 4 (4.5 hours): 2nd Baseline experimental visit (Forearm Blood Flow and Microneurography)

- a. Subject comes to the CRU Human Cardiovascular Research Lab in the CRU between 7-10am after 8 hour overnight fast
- b. Subject will be instrumented with upper arm venous occlusion cuffs and wrist cuffs

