for measurements of forearm blood flow using venous occlusion plethysmography c. A physician trained in brachial artery catheterization in the Human Cardiovascular Research Lab will then perform brachial artery catheterization with 27 G needle and undergo incremental infusions of saline, acetylcholine, acetylcholine + vitamin C (ascorbic acid), and sodium nitroprusside + vitamin C (see Expermental Procedures for details)

- d. Subject will be escorted to Dept of Ophthalmology in Pomerantz Bldg and have picture of retinal performed (scan takes  $\sim$ 10 min)
- e. Subject will be given snack or lunch in CRU.
- f. Subjects will be randomized in a 2:1 scheme to Salsalate or placebo
- g. Nurse will dispense 35 day supply (210 tablets) of Salsalate (dose 3000 mg/day = 500 mg tablets x  $6/\text{day} \times 35 \text{ days} = 210 \text{ tablets}$ ) or placebo
- h. Subject will take first dose of Salsalate (500 mg x 3 pills) or placebo at CRU and 2nd dose (1500 mg) at home in evening- this is Day 0

Visit 5 (45 min) ~Day 14: Subject will return to CRU for venous blood sample to measure serum salicylate (4.5 ml x 2 PST tubes: total 9 ml or ~0.5 tablespoons), Blood pressure, HR and survey of any side effects. If any side-effects/symptoms present, nurse coordinator will follow instructions as outlined in section VIII.2 "Plan for Managing Risks". Subject will receive 3-day food record booklet from CRU bionutritionist

Days 25: Coordinator or research staff will call subject in the evening to remind subject to start 3-day dietary record on days 26, 27, 28.

Visit 6 (5 hours) Betwee Day 26-34: Post-experimental visit #1 (FMD, PWV and Retina)

- a. Subject will take morning dose of Salsalate/placebo and return to CRU between Day 26 -35 for venous blood sample to measure serum salicylate, blood pressure, HR; and survey of any side effects
- b. All vascular measurements of Visit 3 will be repeated
- c. Middle cerebral artery blood flow velocity using transcranial dopper during the following protocol to measure cerebral vasoreactivity to hypercapnia:
- -After 3 min of normal breathing, subjects will perform 2, 30 second breathholds sparated by 3 min.
- -Next, After 3 min of room air breathing, 3 min of breathin 2%CO2, 3 min of breathing 4%CO2 (balanced with 21%O2 and N) will be performed followed by 3 min of room air

breathing.

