- Middle cerebral artery velocity reactivity to hypercapnia: Using non-invasive transcranial doppler ultrasound (TOC Neurovision, Multigon Industries, Inc.), blood flow velocity of the middle cerebral artery (MCA) velocity will be obtained using a 2 MHz doppler probe attached to custom headgear to maintain stable doppler signal. The basal portion of the MCA will be insonated by placing the probe over the temporal bone just above the zygomatic arch between the frontal process and front of the ear. Basal resting velocity will be obtained for 3 minuted followed by 2, 30-second breathholds separated by 1 min. Next, subjects will breathe room air through a Hans-Rudolph mouthpiece with one-way valve (to prevent rebreathing), followed by 3 stepwise increases in end-tidal CO2 (ETCO2) by adding 2%CO2, 4%CO2 and 6%CO2 fractional concentration of CO2 (FiCO2) for 3 minutes each while oxygen content is maintained at 21% and balanced by nitrogen(N). Immediately after the 9 min stepwise increase in FiCO2 trial, the subjects will breathe room air for 3 min to measure MCA velocity recovery. Cerebrovascular reactivity is calculated from the slope of the relation between increases in MCA velocity and ETCO2 in response to stepped increases in FiCO2. ETCO2 will be monitored with a Novametix NICO CO2. monitor attached to the Hans Rudolph mouthpiece, and 3 lead ECG recorded throughout testing.
- c) Brachial artery FMD (endothelium-dependent dilation, EDD) and endothelium-independent dilation. Brachial artery FMD and endothelium-independent dilation will be determined non-invasively using high-resolution ultrasonography (LOGIQ E9, GE Healthcare) as described originally by Celermajer et al. (1992) and more recently by the PI (19, 50, 60, 61). While supine, the subject's arm will be abducted and positioned comfortably on a side table and a pediatric cuff will be secured on the upper forearm (i.e., below the antecubital fold). After selecting a segment of the brachial artery ~3-6 cm above the antecubital fold with clear anterior and posterior intimal-luminal interfaces, the ultrasound probe will be clamped in place to avoid any

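### Cerebral reactivity is tested without nitroglycerin at baseline but is listed straight after it at Visit 6 with no interval stated, so the within-arm change may include a nitroglycerin effect

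*Combined protocol and SAP*

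**What the plan says.** Section VII.E.6 lists the visits step by step, and the form asks the applicant to "Provide a detailed description in sequential order of the study procedures following the consent process".

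- **Baseline.** The test belongs to "Visit 2 (2 hours): Dietary food record, cerebral blood flow velocity". The other items at that visit are diet instruction and fitting of a 24-hour blood pressure monitor. No nitroglycerin is listed.
- **Visit 3.** The vascular series follows a 15-minute supine rest. Its last item is "Brachial artery dilation after 0.3 mg sublingual nitroglycerin with ultrasound".
- **Visit 6.** Step b says "All vascular measurements of Visit 3 will be repeated", with no exception. Step c is "Middle cerebral artery blood flow velocity using transcranial dopper during the following protocol to measure cerebral vasoreactivity to hypercapnia". No interval, washout or return-to-baseline check separates b from c.
- **Nitroglycerin.** The rationale in V.8 says: "The dose is small and has a fast onset of action (1-3 mins) duration of action of 30 min". The flow-mediated dilation (FMD) method gives the tablet ten minutes after FMD and then images for 10 minutes.
- **Outcome.** "Cerebrovascular reactivity is calculated from the slope of the relation between increases in MCA velocity and ETCO2".
- **Analysis (XI.1).** The critical test is the treatment-by-time interaction. Pre v post contrasts within salsalate and within placebo are also planned, as are correlations among changes.

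**The concern.** Visits 2 and 6 supply the only before/after pair for this outcome. As listed, the two tests are done under different conditions: one without a nitric oxide donor, the other in the step after one has been given. The outcome is itself a vasodilator response read from blood velocity. If the Visit 6 test falls within nitroglycerin's action, the change within an arm is the study treatment effect plus whatever nitroglycerin does to the slope. If the time since the tablet varies between subjects, that variation enters the change scores in both arms. It then costs precision in the interaction and in the correlations of change.

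The baseline comparison of prediabetic with non-prediabetic subjects is not touched, because both groups are tested at Visit 2.

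**Working it through.** The plan states no figure on this point, so there is none to reproduce. Two checks apply.

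**1. Timeline from the protocol's own durations**

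Take the tablet as minute 0. Imaging lasts 10 min (FMD method), followed by an unstated gap of g minutes, then the MCA test as set out at Visit 6:

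- Rest, 3 min: 10+g to 13+g
- Two 30-second breath-holds 3 min apart (0.5 + 3 + 0.5 = 4 min): 13+g to 17+g
- Room air, 3 min: 17+g to 20+g
- 2% and 4% CO2, 3 min each: 20+g to 26+g
- Room-air recovery, 3 min: 26+g to 29+g

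The test lasts 3 + 4 + 3 + 6 + 3 = 19 min. The slope uses increases in velocity, which need a reference level, so the relevant span is the room-air period plus the CO2 steps: 17+g to 26+g. Against the stated 30 min:

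- wholly inside if 26 + g ≤ 30, so g ≤ 4;
- CO2 steps wholly outside if 20 + g ≥ 30, so g ≥ 10;
- reference also outside if 17 + g ≥ 30, so g ≥ 13;
- whole test outside if 10 + g ≥ 30, so g ≥ 20.

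For gaps between 10 and 13 min, some or all of the reference is taken under nitroglycerin and the CO2 response is not.

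The methods paragraph on MCA reactivity differs from the visit schedule: it separates the breath-holds by 1 min and adds a 6% CO2 step. It gives no length for the room-air period, so 3 min is assumed throughout.

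| Breath-hold spacing; CO2 steps | Reference | CO2 steps | Both inside 30 min | CO2 outside | Reference outside |
|---|---|---|---|---|---|
| 3 min; 2, 4% | 17+g to 20+g | 20+g to 26+g | g ≤ 4 | g ≥ 10 | g ≥ 13 |
| 3 min; 2, 4, 6% | 17+g to 20+g | 20+g to 29+g | g ≤ 1 | g ≥ 10 | g ≥ 13 |
| 1 min; 2, 4% | 15+g to 18+g | 18+g to 24+g | g ≤ 6 | g ≥ 12 | g ≥ 15 |
| 1 min; 2, 4, 6% | 15+g to 18+g | 18+g to 27+g | g ≤ 3 | g ≥ 12 | g ≥ 15 |

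**2. Which planned tests would be affected**

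Write the mean change as δ + ν under salsalate and ν under placebo, where δ is the drug effect and ν the nitroglycerin shift at Visit 6. The interaction estimates (δ + ν) − ν = δ, so ν cancels. The within-salsalate contrast estimates δ + ν, so it does not. If nitroglycerin acts differently under salsalate by an amount η, the interaction estimates δ + η.

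This was simulated with 20,000 runs, 20 v 10 subjects, δ = 0 and two-sided 5% tests. Shifts are in SDs of the change score. Their sizes are assumptions, because the documents give none.

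| ν (both arms) | η (salsalate only) | Interaction rejects | Within-salsalate rejects |
|---|---|---|---|
| 0 | 0 | 5.2% | 4.9% |
| 0.5 | 0 | 5.0% | 56% |
| 1.0 | 0 | 4.8% | 99% |
| 0.5 | 0.5 | 24.5% | 99% |

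Bias in the interaction is about zero in the first three rows and about 0.5 SD in the last.

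**The case against.** **The order is inferred.** Nothing in the text says the test is done immediately after nitroglycerin. The methods text describes MCA reactivity between pulse wave velocity and FMD, which would put it before the tablet, and the Table 1 attachment is not in the available text. This stands in part. The methods list does not settle the order. It sits under Visit 3, where the schedule has no MCA test. It also places blood chemistries after FMD although blood is drawn earlier, and it describes retinal imaging that the schedule performs at Visit 4. The two sections conflict, and the sequential schedule is the more specific.

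**The gap may be long enough.** Headgear, probe, mouthpiece and monitor must be set up, and a 10-minute gap clears the CO2 steps under the scheduled spacing. This also stands, although the reference period needs about 13 minutes and nothing ensures either. A reader might infer that every randomised completer is tested under nitroglycerin. That assumes a near-zero gap, which the documents do not state. The risk section says nitroglycerin symptoms last 5 to 10 minutes, but that concerns symptoms, whereas the V.8 figure is duration of action.

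**The critical test is protected.** This stands for a shared additive effect. A reader might infer that the salsalate v placebo comparison is confounded. That would require salsalate to alter the cerebral response under nitroglycerin, and the documents give no figure for this, although the trial does measure responses to nitric oxide donors before and after treatment.

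**The outcome is peripheral.** MCA reactivity is in neither Aim, XI.1 does not name it, and XI.2 makes carotid-femoral pulse wave velocity primary. This stands and limits the weight of the point.

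A reader might also infer that fasting or the hold of medicines differs between Visits 2 and 6, because the Visit 3 instruction mentions only experimental visits. VI.13 applies the antihypertensive hold to the morning of testing in general, and the order-of-visits text states the fast and the morning window generally. That reading is not supported.

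**Conclusion.** The concern holds in limited form. As listed, the two tests that make up the only before/after pair for MCA reactivity differ in exposure to nitroglycerin, and the plan does not control the interval. On the visit schedule's figures, reference and CO2 steps lie wholly within the stated 30-minute action for gaps up to 4 minutes and partly within it for gaps up to about 13. Any within-arm pre v post contrast on this outcome is then open to a nitroglycerin effect. If the shared shift were 0.5 SD of change, a null drug would appear active within the salsalate arm in about 56% of trials. Variable timing would add noise to both arms.

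This rests on three assumptions: the schedule is followed in its listed order, imaging ends 10 minutes after the tablet, and the outcome is analysed as XI.1 describes. The interaction is largely protected, and the primary outcome is not involved. This is an avoidable weakness in a non-primary outcome that should be corrected. It does not threaten the trial's main comparison.

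**What to change.** At Visit 6, run the MCA test before the repeated vascular series, then take the 15-minute supine rest that already precedes that series. It has to come before the whole series, because a 19-minute test does not fit in the ten minutes between FMD and nitroglycerin. The alternative is to keep the listed order but start the MCA test only once the stated 30 minutes have passed, which is 20 minutes after imaging ends, within the 5-hour visit. Record the time of the tablet and the start of the test.

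Reconcile the visit schedule with the methods paragraph on the position of the test, the breath-hold spacing and the CO2 steps.

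The first option is a reordering with no new procedure, staff or subjects. Its small drawback is that breath-holds and CO2 would precede FMD at Visit 6 but not at Visit 3. The rest period limits this, and the later-start option avoids it at the price of up to 20 minutes' waiting.

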**Hypothesis 1:** Chronic inflammation inhibition will improve microvascular and large elastic artery function in obese adults with prediabetes.

**Aim 2:** To measure muscle sympathetic nervous system activity (MSNA) and baroreflex sensitivity in obese prediabetic adults before and after 1 month of salsalate or placebo.

**Hypothesis 2:** Chronic inflammation inhibition will decrease MSNA and improve baroreflex sensitivity in obese adults with prediabetes.

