- d. Subject escorted to the CRU Human Cardiovascular Research Lab and a physician or research staff trained in microneurography will insert needle into peroneal nerve for measurement of muscle sympathetic nerve activity
- e. Subject will be instrumented with 24 hour blood pressure monitor to wear home for 24 hours. Subject will return it to the investigators when come in for Visit 7. There is no long term follow up.

Total blood collected for visit 6: 68 (~4.5 Tablespoons)

Visit 7 (3 hours) Between Day 27-35: Post-experimental visit #2

- a. Subject will take morning dose of Salsalate/placebo return to CRU on Day 27 or 28 for venous blood sample to measure serum salicylate, AST/ALT and creatinine (0.5 ml blood)
- b. All measurements from Visit 4 will be repeated
- c. Blood draw for salicylate, insulin, lipid panel, creatinine, ALT/AST (1  $\times$  4.5 ml lt green PST tube)
- d. Total blood collected for visit 7: 4.5 ml ( $\sim$ 1/3 tablespoon)

GRAND TOTAL Blood drawn over course of study: 172 ml (~11.5 tablespoons)

Screening Methods.

- a) Blood pressure, ECG. Subject will undergo resting BP in a private CRU exam room after 15 minutes of rest. BP will be measured in supine position in triplicate separated by 2 min with an automated oscillometric BP machine under quiet, comfortable laboratory conditions. All BPs throughout study will be performed in this identical manner. A resting supine 12-lead ECG will be recorded by placing 10 electrodes on chest and recording the ECG.
- b) History and Physical exam. Prior to the experimental visit (Visit 3), subjects will undergo a complete medical history and physical examination by [name] or a CRU nurse practitioner.
- c) Blood chemistries: After passing the physical exam standard blood chemistry analysis will be obtained under fasting conditions including a basic metabolic panel, lipid panel, HbA1C, complete blood count, TSH and FSH (for women only).

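### As listed, MSNA is recorded under different preceding conditions at baseline (Visit 3) and follow-up (Visit 6), and the plan contradicts itself on which visit supplies the baseline recording

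*Combined protocol and SAP*

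**What the plan says.** Aim 2 (Section I.5) is "To measure muscle sympathetic nervous system activity (MSNA) and baroreflex sensitivity in obese prediabetic adults before and after 1 month of salsalate or placebo". The visit-by-visit account in Section VII.E.6 answers a form item that reads "Provide a detailed description in sequential order of the study procedures following the consent process", so the lettered steps can be taken as a time order.

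- **Visit 2** holds the baseline cerebral test: two breath-holds, then stepped CO2. It is headed "Visit 2 (2 hours): Dietary food record, cerebral blood flow velocity" and involves no nitroglycerin.
- **Visit 3**, second step lettered f, lists the vascular tests. The last is "Brachial artery dilation after 0.3 mg sublingual nitroglycerin with ultrasound". Step g is microneurography: "insert needle into peroneal nerve for measurement of muscle sympathetic nerve activity". The Visit 3 heading does not mention microneurography.
- **Visit 4** is headed "2nd Baseline experimental visit (Forearm Blood Flow and Microneurography", and the methods text describes microneurography under the Visit 4 experimental methods. Visit 4 steps a to h do not contain it.
- **Visit 6**, step b: "All vascular measurements of Visit 3 will be repeated". Step c is the breath-hold and CO2 test. Step d is microneurography, in the same words as Visit 3 step g.
- **Visit 7** repeats everything done at Visit 4.

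The nitroglycerin entry in Section V.8 gives a "fast onset of action (1-3 mins) duration of action of 30 min". The methods text puts a 15-minute beat-to-beat baroreflex recording at Visits 3 and 6 but does not say where in the visit it falls.

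**The concern.** A before/after comparison of nerve activity should be made under the same conditions on both occasions. As listed, two things change between Visit 3 and Visit 6. A breath-hold and CO2 challenge is added before the recording, and the time since nitroglycerin lengthens. The plan itself associates nitroglycerin with transient low blood pressure and low-concentration CO2 with rapid breathing and heart rate (Section VIII.1). Both could plausibly bear on a sympathetic recording made soon afterwards.

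Section XI.1 plans pre/post contrasts within each arm and correlations of change scores, besides the interaction test. A change in the order of procedures could be read as a salsalate effect in the within-arm contrasts.

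Separately, a team working from the visit steps would record baseline MSNA at Visit 3, and a team working from the Visit 4 heading and methods would record it at Visit 4. The pair of recordings that makes up the Aim 2 contrast is therefore not settled.

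**Working it through.** The plan gives no figure on this point to reproduce. The check sets the ordered steps side by side and sums the stated durations.

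**1. Order of steps (Section VII.E.6)**

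| | Baseline | Follow-up |
|---|---|---|
| Vascular tests ending in nitroglycerin | Visit 3, second step f | Visit 6, step b |
| Breath-holds and CO2 | Visit 2, a separate occasion | Visit 6, step c |
| Microneurography | Visit 3, step g | Visit 6, step d |
| Stated rest before the nerve recording | none | none |

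**2. Earliest start of microneurography after the tablet**

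- Imaging after nitroglycerin: 10 min (methods text on brachial dilation).
- Breath-hold and CO2 block in the Visit 6 list: 3 (normal breathing) + 0.5 + 3 + 0.5 (two breath-holds and the gap) + 3 (room air) + 3 + 3 (2% and 4% CO2) + 3 (room air) = 19 min.
- The same block in the methods text: 3 + 0.5 + 1 + 0.5 + 9 + 3 = 17 min, plus a room-air period of unstated length. If that period is 3 min (assumption), the total is 20 min.

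Visit 3: about 10 min. Visit 6: 10 + 19 = 29 min as listed, or 10 + 17 = 27 to 10 + 20 = 30 min by the methods text. Transfer and electrode placement come on top at both visits and are not timed. With a stated action of 30 min, the earliest baseline recording falls well inside the drug's action and the earliest follow-up recording near its end.

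The block itself is described in two ways. The visit list has a 3-minute gap between breath-holds and CO2 steps of 2% and 4%. The methods text has a 1-minute gap and steps of 2%, 4% and 6%. These passages must be reconciled.

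**3. Where an order shift goes in the analysis**

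Let *s* be the mean shift in MSNA change caused by the altered order, and δS and δP the true mean changes on salsalate and placebo.

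- Within salsalate: δS + *s*. Within placebo: δP + *s*.
- Interaction: (δS + *s*) − (δP + *s*) = δS − δP, so a common shift cancels.
- If the shift differs by arm, the difference sS − sP remains in the interaction.
- Change-score correlations: a constant leaves a Pearson correlation unchanged. The part of the carry-over that varies between participants passes into them.

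As an illustration, take no drug effect, 20 v 10 participants, normal change scores, two-sided 0.05 and assumed common shifts:

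| Shift (SD of change, assumed) | Within-salsalate pre/post test rejects | Interaction rejects |
|---|---|---|
| 0 | 5% | 5% |
| 0.25 | 19% | 5% |
| 0.5 | 57% | 5% |
| 1.0 | 99% | 5% |

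This shows where a shift would appear. It is not an estimate of its size.

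**4. Which visits form the MSNA pair**

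- **Visits 3 and 6** (lettered steps): conditions differ, as in 1 and 2.
- **Visits 4 and 7** (Visit 4 heading and methods): neither visit has a CO2 block. MSNA has no stated place among the intra-arterial infusions, and Visit 6 step d has no matching baseline.
- **Visits 4 and 6** (Visit 4 heading with Visit 6 step d): the two visits share no preceding procedures.

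Payment at 15 dollars per hour (Section VII.E.19) gives weak evidence. Visit 3: 60/15 = 4 h against 3 h stated. Visit 4: 45/15 = 3 h against 4.5 h stated. Visit 7, the repeat of Visit 4: 45/15 = 3 h, as stated. This fits microneurography having been moved to Visits 3 and 6 without the Visit 4 heading and methods being updated, but it does not prove it.

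**The case against.** The strongest reply is that the critical test is protected. Section XI.1 rests the main hypotheses on the treatment-by-time interaction. Both arms follow the same order in a double-blind design, and a common shift cancels. This stands. A reader might infer that the treatment effect on MSNA is biased because salsalate could alter the response to nitroglycerin or CO2. That is possible, but nothing in the documents shows it.

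The second reply is that carry-over may be small. The plan says nitroglycerin symptoms pass within about 10 minutes and CO2 symptoms reverse quickly on room air (methods text; Section VIII.1), and the CO2 block ends with 3 minutes of room air. These statements concern symptoms, not nerve activity, so they do not exclude carry-over. They do make its size uncertain.

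Other stronger readings are tempting and not supported:

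- **A loss of power computed from d = 1.06.** That effect size is for carotid-femoral PWV (Section XI.2). PWV is listed first among the vascular tests, before nitroglycerin and CO2, so this carry-over cannot reach it. Section XI.2 gives no effect size for MSNA or baroreflex sensitivity; its Aim 2 calculation is for FMD.
- **All of Aim 2 is mismatched.** The baroreflex recording has no stated position, so a gap in the plan is shown, not a mismatch.
- **Retinal imaging is unmatched.** It is a Visit 4 step and Visit 7 repeats Visit 4. The pair matches; the Visit 3 and 6 headings and the Visit 3 methods placement are wrong.
- **The recording is of resting MSNA.** The visit steps do not say resting, and the microneurography methods include a mental stress test.

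**Conclusion.** The point holds in a limited form. Followed as written, Visits 3 and 6 record MSNA after different preceding stimuli and at different times since nitroglycerin (at least about 10 v 27 to 30 minutes), with no rest interval stated. The plan also contradicts itself on the baseline MSNA visit. That contradiction needs correcting even if carry-over proves negligible.

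The within-arm pre/post contrasts take any common shift in full. The change-score correlations take the part that varies between participants. The interaction is biased only if salsalate alters the carry-over, which is not shown. The documents give no size for the shift, so no effect on power can be stated.

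The conclusion assumes that the lettered steps are a time order and that the vascular tests repeated at Visit 6 include nitroglycerin. Both follow from the plain text.

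**What to change.** 1. Swap steps c and d at Visit 6, so that microneurography follows the vascular tests as at Visit 3 and the cerebral/CO2 test comes last. State one interval between nitroglycerin and the nerve recording, the same at both visits.
2. Give the 15-minute baroreflex recording one fixed position, the same at Visits 3 and 6.
3. Reconcile the headings, steps and methods of Visits 3, 4, 6 and 7 so that one visit pair is named for MSNA. Correct the retinal imaging headings and methods placement to match its Visit 4 and 7 steps. Reconcile the two descriptions of the breath-hold and CO2 block.

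This reorders procedures already planned and adds none. Moving the CO2 test ahead of nitroglycerin at Visit 6 would match Visit 2, but it is not the better choice. The plan gives nitroglycerin ten minutes after FMD, and a block of about 19 minutes does not fit there. It would have to precede FMD, and possibly PWV, at follow-up only, or stretch that interval at follow-up only. Either would move the mismatch onto Aim 1.

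The price of the swap is that the Visit 6 cerebral test still follows nitroglycerin, unlike Visit 2, though after a longer interval than now, and also follows microneurography. The plan should record this as a limitation of the cerebral reactivity comparison.
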